### ***Data Collection Tools***

*Personal Information Form:* The form was administered to determine the participant's socio-demographic characteristics such as age, education level, employment status, family type, income level, and her obstetric characteristics such as whether her pregnancy was planned, what her gestational age was and whether she had undergone NST before.

*Prenatal Comfort Scale (PCS):* Takeishi et al. developed the PCS to determine the prenatal comfort level of the woman in Japan in 2011 [4]. In the first version, the PCS had 34 items, but then they revised it and shortened to 15 items [5]. The short version of the PCS consists of 15 items and the following 5 subscales: "The impact of developing relations with the spouse on the paternity role - Husband" (3,4,7,9), "Interacting with the movements of the fetus - Fetus" (13,14), "Social support received from the people around - People" (11,12,15), "Acceptance of the maternal role and attachment to the baby-Mother" (1,5,8), "Realizing the changes in oneself during pregnancy-Myself" (2,6,10). Response given to the items are rated on a six-point Likert type scale ranging from 0 to 5 (0 = Strongly disagree, 1 = Disagree, 2 = Undecided, 3 = Somewhat agree, 4 = Agree, 5 = Strongly agree). The minimum and maximum possible scores that can be obtained from the PCS are 0 and 75, respectively. The higher the score is the higher the comfort level is. Şenol, Özkan and Aslan performed the validity and reliability study of the Turkish version of the PCS (2020), the Cronbach's alpha value of the PCS was 0.815 in Şenol, Özkan and Aslan's study [6].

*Vital Signs Form:* The form was used to record the pregnant women's body temperature, pulse rate, respiration rate and blood pressure values.

*State Anxiety Scale (SAS):* Spielberger et al. developed the SAS to determine how an individual feels at a certain moment and under certain conditions (1983). Öner and Le Compte performed the validity and reliability study of the Turkish version of the SAS (1998) [7,8]. Some of the items are reverse scored. While the reverse scored items question positive emotions, the other items question negative emotions. Responses given to the items are as follows: "not at all" (1), "somewhat" (2), "moderately" (3), "very much" (4), which indicate the degree of severity of the feelings, thoughts or behaviors. In this section, items 1, 2, 5, 8, 10, 11, 15, 16, 19 and 20 are reverse scored. To calculate the total score of the SAS, the total score of the reversed items is subtracted from the total score of the non-reversed items. Then, 50 points, which is the constant value of the state anxiety scale, are added to this score. The result is the score for the overall SAS. The total score varies between 20 and 80. The higher the score is the higher the level of the anxiety is. While a score ranging between 0 and 19 indicates "no anxiety", a score ranging between 20 and 39 indicates mild anxiety, a score ranging between 40 and 59 indicates moderate anxiety, a score ranging between 60 and 79 indicates severe anxiety, and a score of 80 indicates very severe anxiety (Panic) [8].

### ***Statistical Analysis of the Data***

The data obtained in the present study were analyzed using the SPSS (Statistical Package for Social Sciences) 25.0. In the analysis of the data, to compare the homogeneity between the groups, cross tables were created for categorical variables, and the Chi square ( $\chi^2$ ) and Fisher's exact test were used. Numerical variables were given as mean $\pm$ standard deviation ( $X \pm SD$ ) whereas categorical variables were given as number (n) and percentage (%). For non-parametric data that were not normally distributed, the Mann-Whitney U test was used to evaluate the difference between two groups, and the Kruskal-Wallis H test was used to find differences between the variables with three or more categories. Spearman correlation analysis was performed to reveal the relationship between the dependent variables. The Wilcoxon test (significance test of the difference between two paired groups) was used to test the difference in the dependent groups at two different measurement times. The significance level was accepted as  $p<0.05$ . The confidence interval was 95%.

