## **THE EFFECT OF MUSIC DURING NON-STRESS TESTING ON WOMEN'S COMFORT, VITAL SIGNS AND ANXIETY: A RANDOMIZED CONTROLLED STUDY**

Music has direct and indirect positive effects on the mother and fetus during pregnancy and perinatal period. This study was aimed at investigating effects of music played during the Non-Stress Test (NST) procedure on the mother's comfort, vital signs and anxiety.

The present study is a randomized controlled experimental study. Pregnant women who presented to the NST outpatient clinic of a research hospital in the Central Anatolia region of Türkiye between June 2025 and August 2025 comprised the population of the study. The study's sample size was calculated using the G\*Power 3.1.9.2 software based on data from a study by Baskurt and Yilmaz [1]. The mean anxiety scores and standard deviation values from that study were used, and the effect size was calculated as 0.79. The minimum number of pregnant women to be included in the sample of this study was calculated as 70 pregnant women, 35 in each group, using the G\*Power 3.1.9.2 software, based on an effect size of 0.79, an alpha value of 0.05, and a power value of 0.95. To increase the analysis power of the study, the study sample consisted of 173 pregnant women (music group= 93 and control group= 80).

The inclusion criteria of the study were as follows: being between the ages of 18 and 45 years, having completed the 32nd week of gestation, not having any risk factors in their pregnancy (such as premature rupture of membranes, preeclampsia, gestational diabetes), not having multiple pregnancies, not having low (80/60 mmHg and below) or high (140/90 mmHg) blood pressure levels, having eaten at least two hours before the NST procedure, not smoking or consuming alcohol at least two hours before the NST procedure, being able to communicate, not having any hearing problems, and volunteering to participate in the study.

The exclusion criteria of the study were as follows: Pregnant women who had a fetus with fetal distress, for whom emergency intervention was considered by the physician, who had impaired NST and required immediate intervention, who had a psychiatric disease diagnosis and hearing impairment were not included in the study (Figure 1).

**Figure 1.** CONSORT flowchart

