### *Data collection:*

The data of the study were collected from the pregnant women using the face-to-face interview technique at the NST outpatient clinic on the days and hours when the researcher was present in the hospital. The participating pregnant women were not informed of the group they belonged to. Since only the researcher knew the participants' groups, single-blindness was achieved in the study.

*Music Group:* The purpose of the study was explained to the pregnant women who met the inclusion criteria. After their written consent was obtained, they were administered the Personal Information Form, Prenatal Comfort Scale, Vital Signs Form, and State Anxiety Scale used to measure their anxiety level before the NST procedure. They were asked to lie on their left or right side. After the pregnant women were positioned, while the NST procedure was implemented they listened to music for 20-30 minutes. The pregnant women listened to the music on an MP3 player during the application. The duration of the music recorded on the

MP3 player was 30 minutes. To avoid hygiene problems, each pregnant woman was provided with individual headphones, which were given to them as a gift after the procedure. The volume of the music was adjusted by the pregnant women. After the procedure was completed, the Prenatal Comfort Scale, Vital Signs Form and State Anxiety Scale were administered again.

*Control Group:* The purpose of the study was explained to pregnant women who met the inclusion criteria. After their written consent was obtained, they were administered the Personal Information Form, Prenatal Comfort Scale, Vital Signs Form, and State Anxiety Scale used to measure their anxiety level before NST. They were asked to lie on their left or right side. They underwent no other intervention during the NST procedure. After the procedure was completed, the Prenatal Comfort Scale, Vital Signs Form and State Anxiety Scale were administered again.

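### Outcomes are measured before and after the NST in both arms, but the plan names no baseline-adjusted between-arm analysis, no score for Mann-Whitney, and no between-arm estimate for its 95% CI

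*Combined protocol and SAP*

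**What the plan says.** - **Measurements.** Under Data collection, both arms complete the State Anxiety Scale (SAS), the Prenatal Comfort Scale (PCS) and the Vital Signs Form before the NST. The same sentence then appears for each arm: "After the procedure was completed, the Prenatal Comfort Scale, Vital Signs Form and State Anxiety Scale were administered again". Data Collection Tools lists the vital signs as "body temperature, pulse rate, respiration rate and blood pressure values".
- **Between-arm test.** Statistical Analysis of the Data opens its two-group provision with "For non-parametric data that were not normally distributed" and continues "the Mann-Whitney U test was used to evaluate the difference between two groups". It names no outcome and no score (post or change).
- **Other methods.** Chi-square and Fisher's exact tests are for group homogeneity, Kruskal-Wallis for three or more categories, Spearman for correlations, and Wilcoxon for the two time points in dependent groups. Wilcoxon is the only method explicitly tied to both time points, and it does not compare music with control. There is no ANCOVA, regression, mixed model or group-by-time test.
- **Reporting.** "Numerical variables were given as mean" with standard deviation, and "The confidence interval was 95" percent. No contrast is attached to that interval.
- **Sizing.** The opening section states: "The mean anxiety scores and standard deviation values from that study were used, and the effect size was calculated as 0.79". This gave a minimum of 70 women; 173 (93 music, 80 control) were taken, to raise power.

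**The concern.** When each woman has a baseline value of the outcome itself, part of the post-test spread is simply the spread she arrived with. Adjusting for it sharpens the comparison of arms at no cost in recruitment. The plan holds these data for every outcome and does not use them in this way. Three things are at stake:

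1. **Precision** for effects smaller than 0.79 SD, and for PCS and vital signs, which played no part in the sample-size calculation.
2. **An estimate.** A Mann-Whitney p-value does not say how much music changed anxiety, comfort or pulse, or how uncertain that amount is.
3. **A fixed question.** With the score unnamed, post and change are both open, and they can give different answers.

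**Working it through.** **Inputs from the documents:** 93 and 80 women; effect size 0.79; alpha 0.05; power 0.95; stated minimum 35 per arm.

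**Assumptions, not in the documents:** pre-post correlation r from 0.4 to 0.7; equal SD before and after; a smaller true effect of 0.4 SD; the data shapes named below.

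**1. The plan's own figure.** Per arm, n = 2(z_alpha + z_power)²/d².
- One-sided: 2(1.645 + 1.645)²/0.79² = 34.7, so 35 per arm. This matches the stated 70 (exact t calculation: 36).
- Two-sided: 2(1.960 + 1.645)²/0.79² = 41.6, so 42 per arm (exact t: 43).

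The stated figure fits a one-sided, unadjusted two-group comparison. Sidedness is a separate matter and nothing below depends on it.

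**2. Power at the planned effect.** SE = √(1/93 + 1/80) = 0.1525 SD, and 0.79/0.1525 = 5.18. Two-sided power is 0.999 for the t-test, and also 0.999 for Mann-Whitney with its normal-data efficiency of 0.955. There is no shortage of power at 0.79 SD.

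**3. Variance in units of SE².** Post score: 1. Change score: 2(1 − r). Baseline-adjusted: 1 − r². Adjusted against change is therefore (1 − r²)/[2(1 − r)] = (1 + r)/2. Half-widths are 1.96 × 0.1525 × the square root of the variance factor.

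| r | Cut vs post | Cut vs change | 95% CI half-width: post / change / adjusted (SD) | Unadjusted post-score N equal to 173 adjusted, 173/(1 − r²) |
|---|---|---|---|---|
| 0.4 | 16% | 30% | 0.299 / 0.327 / 0.274 | 206 |
| 0.5 | 25% | 25% | 0.299 / 0.299 / 0.259 | 231 |
| 0.6 | 36% | 20% | 0.299 / 0.267 / 0.239 | 270 |
| 0.7 | 49% | 15% | 0.299 / 0.232 / 0.213 | 339 |

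Outside that range, the cut against post scores is 4% at r = 0.2 and 72% at r = 0.85; against change scores it is 7.5% at r = 0.85.

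**4. Power at an assumed 0.4 SD.** Simulation with 93 vs 80 women, 6,000 runs, r from 0.4 to 0.7:

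| Shape | Mann-Whitney post | Mann-Whitney change | Linear ANCOVA | Rank (Quade) ANCOVA |
|---|---|---|---|---|
| Normal | 0.718–0.722 | 0.637–0.907 | 0.803–0.955 | 0.782–0.934 |
| Mild skew, gamma(4) | 0.800–0.807 | 0.685–0.931 | 0.806–0.946 | 0.863–0.965 |
| Exponential | 0.963–0.968 | 0.825–0.984 | 0.798–0.932 | 0.979–0.999 |
| t, 3 df | 0.944–0.947 | 0.834–0.978 | 0.828–0.935 | 0.969–0.998 |
| Lognormal | 0.992–0.994 | 0.916–0.998 | 0.794–0.915 | 0.997–1.000 |

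Formula check for normal data at r = 0.4 and 0.7: Mann-Whitney post 0.727 at both; Mann-Whitney change 0.648 and 0.911; linear ANCOVA 0.817 and 0.957. These agree with the first row.

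For an SAS-like integer score bounded at 20 and 80 (assumed mean 37, SD 10, skewed; 3,000 runs), power is 0.82 for Mann-Whitney post, 0.80–0.94 for linear ANCOVA and 0.88–0.98 for rank ANCOVA. Change scores were not simulated for that shape.

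**5. Error rate if the score is chosen afterwards.** With no effect, the post and change statistics correlate at √((1 − r)/2), that is 0.548 at r = 0.4 and 0.387 at r = 0.7. The chance that at least one passes the two-sided 5% level is then 8.9% and 9.4%. The simulations gave 8.3–9.8%, against 4.1–5.6% for any single test.

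**The case against.** **Randomization makes the unadjusted test valid, and power at 0.79 SD is about 99.9%.** This stands. A reader might infer that omitting baseline makes the comparison biased or wrong. It does not, on either score.

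**The gain depends on which score was tested.** This stands. A reader might take the normal-data move from 0.72 to 0.96 as the gain, but that is against post scores at r = 0.7. If change scores were used, the figures at the same r are 0.907 against 0.955 (linear) or 0.934 (rank). At r = 0.4 the order reverses, and change scores are the weaker comparator.

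**Means, SDs and group sizes are available.** This stands in part. A reader might infer that the trial cannot report the quantity it was sized on, but an unadjusted mean difference and an approximate CI can be derived from what is reported. No between-arm or baseline-adjusted estimate with a CI is planned.

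**ANCOVA suits normal data, and the plan provides for non-normal data.** This stands for linear ANCOVA as a test: it loses to Mann-Whitney under heavy skew or heavy tails. It does not stand for rank ANCOVA, which was no worse than either Mann-Whitney version in every shape where both were run.

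**The study reads as finished.** "The data obtained in the present study were analyzed" is in the past tense. New wording cannot restore prespecification if results have been seen, but it can still make the report clearer.

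**Conclusion.** The point holds as a loss of precision of unknown size, together with a missing estimate and an unnamed score. It is neither bias nor an error in the test. Moderate priority: worth changing, but it does not invalidate the comparison.

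The percentages rest on an assumed r of 0.4 to 0.7, equal SDs and roughly normal data; the power figures also assume a 0.4 SD effect. The documents supply none of these, and one range of r need not suit SAS, PCS and each vital sign alike.

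A reader might also infer that post or change was picked to suit the result. The documents give no sign of that; the 8 to 10% figure describes what the open choice would permit.

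**What to change.** In Statistical Analysis of the Data:

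1. For SAS, PCS and each vital sign, compare the arms on the post-NST score adjusted for that measure's own baseline.
2. Because the plan expects non-normal data, state rank (Quade) ANCOVA as the one test for every outcome, with no switch driven by the data. It ranks both scores over all women, regresses post ranks on baseline ranks, and compares the residuals between arms.
3. Report the baseline-adjusted mean difference from linear ANCOVA with a robust or bootstrap 95% CI, and say that this is what the interval refers to.
4. Keep Mann-Whitney as a sensitivity analysis on one named score, post or change.
5. If results have already been seen, label the adjusted analysis as post hoc and keep the original test in the report.

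**Cost:** one extra model per outcome on data already collected, with no further participants. The rank test and the mean-difference CI answer slightly different questions and can occasionally disagree when data are skewed; the report should say so in advance. Robust or bootstrap errors protect the validity of the interval but do not recover power.

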### *Randomization:*

Simple randomization method was used in this study. Pregnant women who met the study criteria were randomly assigned to the music or control group with equal probability, independently of any previous assignments, on the day they came to the hospital for their physical examination. The total number of pregnant women determined by the G\*Power analysis was entered into the program at "<https://www.randomizer.org/>," and randomization was conducted using the program. The assignment of the groups was performed on the computer, and the pregnant women were randomly assigned to the music and control groups.

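### The Spearman correlations between outcomes name neither arm nor time point; if run over both arms on after-NST or change scores, a music effect on both outcomes would by itself produce a correlation

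*Combined protocol and SAP*

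**What the plan says.** In the combined protocol and SAP, the section Statistical Analysis of the Data gives the correlation analysis one sentence: "Spearman correlation analysis was performed to reveal the relationship between the dependent variables". It mentions no arm, stratification, adjustment or time point. The same section sets one rule for all tests: "The significance level was accepted as" p<0.05. Nothing marks the correlations as exploratory.

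The outcomes are state anxiety (SAS), prenatal comfort (PCS) and the vital signs. The Data collection section has each of them recorded in both arms before the NST and again after it. The opening section gives 173 women, 93 in the music arm and 80 in the control arm. Its only effect size is for anxiety: "The mean anxiety scores and standard deviation values from that study were used, and the effect size was calculated as 0.79". No effect size is given for comfort or for any vital sign.

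**The concern.** The trial looks for an effect of music on several outcomes at once. Suppose music lowers anxiety and raises comfort. After the NST, women in the music arm then tend to have lower anxiety and higher comfort than women in the control arm. One coefficient over all 173 women picks up that separation as a negative correlation, even if a more anxious woman is no less comfortable than others in her own arm.

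A significant coefficient could then be reported as a link between anxiety and comfort, or between anxiety and pulse, when it only restates the treatment effect. The distortion arises when music moves both outcomes, which is the result the trial hopes for.

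**Working it through.** **The plan's own figure.** The sample size was "based on an effect size of 0.79, an alpha value of 0.05, and a power value of 0.95", and the minimum "was calculated as 70 pregnant women, 35 in each group". Treating 0.79 as a standardised mean difference, the normal formula gives n per group = 2(z_alpha + z_beta)²/d².
- One-sided: 2(1.645 + 1.645)²/0.6241 = 34.7, so 35.
- Two-sided: 2(1.960 + 1.645)²/0.6241 = 41.6, so 42.

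The stated 35 is reproduced with a one-sided test (36 with the t distribution). For this point it matters only that 0.79 behaves as a difference in SD units.

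**Inputs.**
- From the documents: arms of 93 and 80, significance level 0.05, d1 = 0.79 for anxiety.
- Assumed: two-sided Spearman test; normal outcomes; zero correlation within each arm; a shift d2 in the second outcome, varied because the documents give none. Shifts are in within-arm SDs of the score that is correlated.

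**Induced correlation.** With p = 93/173 = 0.5376, p(1−p) = 0.2486. For outcomes unrelated within arm, the pooled Pearson correlation is

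r = p(1−p)·d1·d2 / √[(1 + p(1−p)·d1²)(1 + p(1−p)·d2²)].

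At d1 = d2 = 0.79: 0.2486 × 0.6241 = 0.1551, and r = 0.1551/1.1551 = 0.134. Opposite shifts give −0.134.

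**False-positive rates.** 40,000 simulated trials per row, arms 93/80, d1 = 0.79. The adjusted test correlates ranks after removing arm means.

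| d2 | Mean pooled Spearman | Pooled, p<0.05 | Arm-adjusted, p<0.05 | Music arm only, p<0.05 |
|---|---|---|---|---|
| 0 | 0.000 | 0.0500 | 0.0509 | 0.0481 |
| 0.2 | 0.035 | 0.0748 | 0.0513 | 0.0487 |
| 0.3 | 0.053 | 0.1052 | 0.0500 | 0.0503 |
| 0.5 | 0.087 | 0.2047 | 0.0493 | 0.0496 |
| 0.79 | 0.134 | 0.4185 | 0.0498 | 0.0492 |
| −0.79 | −0.133 | 0.4203 | 0.0520 | 0.0488 |

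**Hand check of the 0.79 row.** By Fisher's z, atanh(0.1336) × √(173 − 3) = 0.1344 × 13.04 = 1.752. The chance of exceeding 1.960 is P(Z > 0.208) = 0.418, which agrees with the simulation.

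**Other settings (pooled, 93/80 unless stated).**
- No shift in either outcome, as for before-NST scores: 0.0504.
- 0.3 SD on both: 0.0590. 0.5 SD on both: 0.1143.
- 1.0 SD on both: 0.7650. 0.79 with 1.2 SD: 0.7177.
- 0.79 SD on both at the planned minimum of 35 per arm: 0.1979.

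**Outcomes that are related.** The size of the coefficient is distorted too. With a within-arm Pearson correlation of −0.20 and opposite shifts of 0.79 SD, the pooled value is (−0.20 − 0.1551)/1.1551 = −0.31.

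**The case against.** **Pooling is inferred from silence.** This is correct. A reader might infer that the plan pools the arms, because it names a test for comparing groups and another for paired measurements but sets no arm condition on the correlation. The contrast does not bear that weight: the Wilcoxon sentence concerns paired measurements and names no arm either. The time point is equally unstated, and within-arm or before-NST correlations would carry no inflation. What remains is that the plan does not exclude the distorted version.

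**The 42% borrows an effect size.** Also correct. The 0.79 belongs to anxiety. The PCS covers matters such as the relationship with the spouse and support from others, and nothing in the documents supports a shift of that size after 20 to 30 minutes of music. Hence the range for the second outcome.

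**A pooled correlation may be a legitimate target.** If music moves both outcomes, their correlation in the mixed sample is truly non-zero, so calling it a false positive presumes that the within-arm relationship is wanted. The plan does not say which is meant. Still, the pooled value depends on the treatment effects and the arm sizes, and so does not isolate how the outcomes relate among women treated alike.

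**Kruskal-Wallis.** A reader might extend the point to the sentence that "the Kruskal-Wallis H test was used to find differences between the variables with three or more categories". The documents do not support this. They do not say which scores or categories are tested, and women were "randomly assigned to the music or control group with equal probability", so arm is independent of baseline categories in expectation. Ignoring arm there adds noise but no systematic association.

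**Conclusion.** The concern holds conditionally. Three things must coincide: the correlations are run over both arms, on after-NST or change scores, and music shifts both outcomes. For 93 and 80 women, no within-arm correlation and 0.79 SD on anxiety, the false-positive rate is then about 5% to 42% as the assumed second effect goes from 0 to 0.79 SD. Remove any one condition and it is about 5%.

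Two stronger readings are not supported. The 42% is neither the plan's error rate nor a ceiling: it is the result at one assumed second effect, and larger effects exceed 70%. Nor does the point weaken the trial's main results. No hypothesis, primary outcome or sample-size calculation in the documents rests on the correlation, and the between-arm comparisons are unaffected. This is an underspecified secondary analysis with a simple, better alternative.

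**What to change.** Amend the correlation sentence in Statistical Analysis of the Data to:
- state the time point (before NST, after NST, or change);
- report a partial Spearman correlation adjusted for arm, computed on ranks, or a Spearman coefficient within each arm;
- label the correlations exploratory.

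If only before-NST scores were used, saying so is enough to remove the inflation.

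The cost is one sentence and a re-run in SPSS, with no new data. Adjusting for arm uses all 173 women. Reporting by arm loses some precision: the approximate standard error of Fisher's z rises from 1/√170 = 0.077 to 1/√90 = 0.105 in the music arm and 1/√77 = 0.114 in the control arm. The adjusted coefficient is therefore the better default, with the within-arm values alongside if the relationship may differ between arms.

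### Before-after change is given only a paired within-arm test, and the plan does not say which test decides whether music had an effect

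*Combined protocol and SAP*

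**What the plan says.** The opening description sets the aim: "This study was aimed at investigating effects of music played during the Non-Stress Test (NST) procedure" on comfort, vital signs and anxiety. The design is randomised, with women "randomly assigned to the music or control group with equal probability", and "the study sample consisted of 173 pregnant women (music group= 93 and control group= 80". Under Data collection, both arms complete the Prenatal Comfort Scale (PCS), the Vital Signs Form and the State Anxiety Scale (SAS) before and after the NST.

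Statistical Analysis of the Data then names:

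- a paired Wilcoxon test, which "was used to test the difference in the dependent groups at two different measurement times". That this means one test within each arm is an inference, though the natural one;
- a between-group test: "For non-parametric data that were not normally distributed", "the Mann-Whitney U test was used to evaluate the difference between two groups". The sentence does not say whether it applies to baseline, post-NST or change scores, and no test is named for normally distributed data;
- one threshold for everything: "The significance level was accepted as" p<0.05, with sidedness not stated.

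The section names no between-arm test of change, no baseline-adjusted comparison, no primary outcome and no deciding test.

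**The concern.** The effect of music is a difference between the randomised arms. A paired test in one arm asks only whether scores moved in that arm. They can move in both arms for reasons unrelated to music: the procedure is over, the woman has been lying on her side, extreme first scores drift back, or the same questionnaire is being answered a second time. Finding p<0.05 in one arm and not in the other does not test the difference between them, and the larger music arm reaches p<0.05 more easily for the same change.

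The plan leaves a reader with paired p-values for change, an incompletely defined between-group p-value, all at 0.05, and no rule for when they disagree. If the paired results were contrasted, the protection of randomisation would be lost and the error rate could be well above the nominal 5%.

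**Working it through.** **The plan's own figure first.** The sample size is "based on an effect size of 0.79, an alpha value of 0.05, and a power value of 0.95", giving 70 women, 35 per group. With n per arm = 2(z_alpha + z_power)²/d²:

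- one-sided: 2(1.645 + 1.645)²/0.79² = 34.7, so 35 per arm, which matches;
- two-sided: 2(1.960 + 1.645)²/0.79² = 41.6, so 42 per arm.

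The figure reproduces only as a one-sided calculation. This matters here because the sidedness of the analysis level is not stated either. I assume two-sided 0.05 below and check one-sided at the end.

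**Inputs.** Arm sizes 93 and 80 (opening description); level 0.05 (Statistical Analysis of the Data). Assumed, because the documents give no figure: a true before-after shift δ, in SDs of the change score, identical in both arms, so that the effect of music is zero; normally distributed changes; independent arms.

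**Formula.** The probability that an arm of size n is significant is, by normal approximation,

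P(n, δ) = Φ(δ√n − 1.96) + Φ(−δ√n − 1.96),

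and the probability of the misleading pattern (music significant, control not) is P(93, δ) × [1 − P(80, δ)].

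**No shift.** 0.05 × 0.95 = 0.0475. This counts significant changes in either direction.

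**Near the peak, δ = 0.216.**

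- Music: 0.216 × √93 = 2.083; Φ(2.083 − 1.96) = 0.549.
- Control: 0.216 × √80 = 1.932; Φ(1.932 − 1.96) = 0.489.
- Pattern: 0.549 × (1 − 0.489) = 0.281.

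The noncentral t gives the same maximum, 28.1%, at δ = 0.218 (0.548 × (1 − 0.487)).

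**Over the range of δ.** The Wilcoxon columns come from 40,000 simulated trials per value. The last column is a Mann-Whitney test on change scores between arms, from 8,000 trials per value.

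| Shared shift (SD of change) | Music-only, noncentral t | Music-only, simulated Wilcoxon | Mann-Whitney on change |
|---|---|---|---|
| 0 | 4.8% | 4.7% | 4.8% |
| 0.10 | 13.6% | 13.3% | 4.6% |
| 0.20 | 27.6% | 27.3% | 4.6% |
| 0.22 | 28.1% | 28.4% | 5.0% |
| 0.30 | 20.0% | 21.2% | 5.1% |
| 0.40 | 5.6% | 6.5% | 5.3% |
| 0.50 | 0.7% | 0.8% | 5.2% |

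The curve rises and falls because the pattern needs one arm to pass and the other to miss. That is most likely when each arm has about a 50% chance of significance, and rare when both almost always pass.

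**Sensitivity.** With equal arms the peak is 25.0%, so the excess over 25% comes from the unequal split. With one-sided 0.05 the peak is 27.6% at δ = 0.184. Neither changes the conclusion.

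**The case against.** The strongest reply is that the plan does contain a between-group test. There are only two randomised arms, so the natural reading of the Mann-Whitney sentence is music against control; applied to post-NST scores, that is a valid randomised comparison at about 5%. This stands. A reader might infer that the plan has no between-arm comparison at all, and the documents do not support that. What remains is narrower: the test is not linked to a score or time point, it is conditional on non-normality, and the same sentence goes on to the Kruskal-Wallis test for variables with three or more categories, so it can also be read as covering participant characteristics.

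A second reply is that no decision rule based on two paired p-values appears anywhere in the plan. This also stands. A reader might infer that 28% is the plan's false-positive rate. It is not: it is the worst case of a reading that the plan neither states nor forbids, at a shift that the documents do not give.

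A third tempting inference is that a false music finding is almost certain across seven outcomes (SAS, PCS, temperature, pulse, respiration, systolic and diastolic pressure). In simulations with paired t-tests, at least one music-only pattern occurs in about 70% (correlation 0.5) to 90% (independent) of trials if every outcome shifts by 0.20 SD. The same calculation gives about 23% to 28% at no shift, 23% to 32% at 0.40 SD and 4% to 5% at 0.50 SD. Nothing in the documents supports one near-worst-case shift for all seven, and the figure mixes in multiplicity, which is a separate matter.

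**Conclusion.** The concern holds as a gap in the plan. The only test tied to before-after change does not address the stated aim, and nothing says which test decides. The size is conditional: if the paired results were contrasted, the false-positive chance per outcome would run from under 1% to about 28%, depending on an unknown shared shift, with about 5% at no shift. A between-arm test of change holds 4.6% to 5.3% at every shift tested. These figures rest on 93 and 80 women, two-sided 0.05, normal change scores and the same shift in both arms. The gap should be closed before results are interpreted, but it does not show that the trial's conclusions will be wrong.

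**What to change.** In Statistical Analysis of the Data:

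1. Name the music-versus-control comparison on which any claim about music rests, for SAS, PCS and each vital sign: the post-NST score adjusted for its own baseline value, or a Mann-Whitney test on the change score. State which of the two is used, and that the test is two-sided.
2. Label within-arm before-after changes as descriptive, reported as the change with its 95% CI, and state that they can neither support nor override the between-arm result.

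The cost is a few sentences and a re-run on data already in the plan, since both measurements are taken in both arms. The downside is that within-arm p-values can no longer be quoted as evidence for music. If outcome data have already been seen, the date of the change should be recorded.
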